**5.3.5.3 Visit 6 (Day 42) and Visit 7 (Day 49, EOS) – Clinic/Classroom Days**

Amendment 4: Version 5.0 May-08-2013

Amendment 3: Version 4.0 December-11-2012

Amendment 2: Version 3.0 October-31-2012

Amendment 1: Version 2.0 August-02-2012

Final Protocol May-25-2012

Subjects will return to the clinic for evaluations on Day 42 and Day 49. The following evaluations will be performed during each clinic visit:

1. Record any AEs or concomitant therapy since previous visit.
2. Perform drug accountability and collect all used and unused patches
3. Review the daily dosing and daily dermal evaluation diaries for compliance.
4. Obtain vital signs (sitting BP, HR, RR, oral body temperature) within 30 minutes pre-dose and 4 and 12 hours  $\pm$  30 min post-dose
5. Record weight (Day 49 only)
6. Collect blood and urine for clinical laboratory assessments (Day 49 only)
7. Perform a complete physical exam (Day 49 only)
8. Perform 12-lead ECG
9. Perform urine pregnancy testing on all female subjects of child-bearing potential.
10. Patch application by subject/parent/caregiver/site personnel.
11. Patch removal at 9 hours by site personnel
12. Evaluate adhesion and discomfort at 1, 2, 4, 8 and 9 (prior to patch removal) hours after d-ATS patch application.
13. For discomfort scores greater than 0, discomfort will also be evaluated at 1, 2, 4, 8 and 9 (prior to removal) hours after d-ATS patch application using the 10-point Wong-Baker Faces or Visual Analog Scale (age dependent). A  $\pm$  15 minute window is permissible.
14. Evaluate skin irritation prior to patch application and at 30 minutes, 1 and 3 hours after patch removal.
15. Evaluate skin irritation of the previous day's patch 24 hours after its removal
16. Examine and grade for adhesive residue immediately following patch removal
17. Obtain ADHD-RS-IV (home version) score (may be obtained the same or prior day).

Amendment 4: Version 5.0 May-08-2013

Amendment 3: Version 4.0 December-11-2012

Amendment 2: Version 3.0 October-31-2012

Amendment 1: Version 2.0 August-02-2012

Final Protocol May-25-2012

18. Laboratory classroom – perform SKAMP and PERMP: within 30 minutes prior to dosing and at 1, 2, 3, 4.5 (4½), 6, 7, 9, 10, and 12 hours following administration of study drug (SKAMP and PERMP rating periods will be 20 minutes in duration).
19. Perform CGI-I
20. Administration of the C-SSRS (Children's Since Last Visit version) by a trained staff member
21. On Day 42, contact IVRS/IWRS to obtain study medication pack number. After receiving the pack number, prior to dispensing, remove one pouch from the medication pack, fill in applicable subject information on the label, and retain the pouch for application in the clinic on Day 49.
22. Dismiss from clinic
23. On Day 49, contact IVRS/IWRS to complete the subject in the system.

### **5.3.6 *Early Termination***

If the subject is discontinued early (prior to Day 49), the following procedures will be performed:

1. Record any AEs or concomitant therapy since previous visit.
2. Perform drug accountability and collect all used and unused patches.
3. Obtain vital signs (sitting BP, HR, RR, oral body temperature).
4. Obtain weight.
5. Collect blood and urine for clinical laboratory assessments
  - Complete Blood Count (including differential and platelet count)
  - Blood Chemistry
  - Urinalysis
6. Perform a 12-lead electrocardiogram (ECG) prior to discharge.
7. Perform complete physical examination
8. Perform urine pregnancy testing on all female subjects of child-bearing potential.

Amendment 4: Version 5.0 May-08-2013

Amendment 3: Version 4.0 December-11-2012

Amendment 2: Version 3.0 October-31-2012

Amendment 1: Version 2.0 August-02-2012

Final Protocol May-25-2012

9. Obtain ADHD-RS-IV score.
10. Perform CGI-I.
11. Administration of the C-SSRS (Children's Since Last Visit version) by a trained staff member.
12. Dismiss from clinic.
13. Contact IVRS/IWRS to early discontinue the subject in the system.

### **5.3.7 *ADHD Treatment after Study Completion or Early Withdrawal***

At the end of the study or at early withdrawal the investigator (in consultation with the subject/parent/caregiver) may resume the subject's usual ADHD treatment. In the event that the subject experiences intolerable side effects or the subject's ADHD symptoms worsen while in the study, the subject may be discontinued from the study and their usual ADHD treatment may be resumed at the discretion of the investigator (in consultation with the subject/parent/caregiver). The investigator may continue to provide up to 3 months care for behavior and medication management.

### **5.3.8 *Follow-up Telephone Contact (Visit 8, Week 8, Day 56 + 3 days)***

A study staff member will call subjects/parent/caregiver 7-10 days after last dose of study drug to inquire about and record any AEs and concomitant therapy since last visit.

## **6 DESCRIPTION OF ASSESSMENTS**

Study procedures are detailed below and summarized in APPENDIX 1.

### **6.1 SKAMP AND PERMP**

The efficacy assessment is the Swanson, Kotkin, Agler, M-Flynn and Pelham Rating Scale (SKAMP) – Teacher Rating Scale (Appendix 5) to evaluate behavioral effects of d-ATS compared to placebo measured at multiple time points throughout the study. The SKAMP scale is a validated rating scale that assesses behavioral symptoms of ADHD in a classroom setting using a 7-point impairment scale (0 = none, 6 = maximal impairment). The SKAMP total score comprises 13 items. The SKAMP was designed for independent observers to rate 13 items representing two factors of classroom behavior: attention and deportment. Each item is rated on a

Amendment 4: Version 5.0 May-08-2013

Amendment 3: Version 4.0 December-11-2012

Amendment 2: Version 3.0 October-31-2012

Amendment 1: Version 2.0 August-02-2012

Final Protocol May-25-2012

7-point scale. Items are specific to place (classroom setting) and time (during a typical classroom period) and the scale is used to assess multiple ratings taken within a day. The SKAMP-D subscale evaluates deportment, including interacting with other children, interacting with adults, remaining quiet according to classroom rules, and staying seated according to classroom rules. The SKAMP-A subscale is a measure of attention and evaluates getting started on assignments, sticking with tasks, attending to an activity, and making activity transitions. The SKAMP quality of work subscale includes 3 items: completing assigned work, performing work accurately, and being careful and neat while writing or drawing.

For consistency among clinical sites, SKAMP and PERMP will be measured in three (3) laboratory classroom sessions during the Day 35 (Visit 5, practice) laboratory school study day, and ten (10) laboratory classroom sessions on each of Day 42 (Visit 6) and Day 49 (Visit 7). Additionally, a classroom schedule will be developed for all clinical sites to follow in an effort to standardize timing of activities and transition times to the classroom rating periods. Each approximately 30-minute laboratory classroom session is specified to include a 20-minute rating period with a buffer of up to 10 minutes within the classroom for transitional games surrounding the rating period.

The other efficacy assessment is the Permanent Product Measure of Performance (PERMP) Derived Measures (Appendix 6), an age-adjusted math test to assess the duration of efficacy of ATS compared to placebo administered at multiple time points during the study. The PERMP is a ten-minute written test performed as seatwork in a classroom. Subjects are given five pages of 80 math problems (400 total problems) and are instructed to work at their desks and to complete as many problems as possible in 10 minutes. Performance is measured as the number of problems worked correctly and the number of problems attempted. Different versions will be used among subjects to adjust for ability as determined by the math pre-test at the baseline visit (Day 0). Additionally different versions will be used across classroom cycles so that a subject does not take the same test more than once during the day. A stopwatch should be used to time the test.

## **6.2 ADHD-RS-IV (Home Version)**

The ADHD-RS-IV is a clinician-rated scale that reflects current symptoms of ADHD based on Diagnostic and Statistical Manual of Mental Disorders, Fourth Edition, Text Revision (DSM-IV-

Amendment 4: Version 5.0 May-08-2013

Amendment 3: Version 4.0 December-11-2012

Amendment 2: Version 3.0 October-31-2012

Amendment 1: Version 2.0 August-02-2012

Final Protocol May-25-2012

TR) criteria; it is a global assessment that measures the severity of symptoms from visit to visit, but was not used to assess symptoms of ADHD over the course of the day. The ADHD-RS-IV was developed to measure behaviors of children with ADHD and it consists of 18 items designed to reflect current symptomatology of ADHD based on DSM-IV criteria. Each item is scored from a range of zero (reflecting no symptoms) to three (reflecting severe symptoms) with total scores ranging from 0 to 54. The 18 items may be grouped into two sub-scales: hyperactivity/impulsivity (even number of items numbered 2 through 18) and inattentiveness (odd number of items numbered 1 through 17). Investigators will use the ADHD-RS-IV: Home Version by gender scoring sheet to determine eligibility.

### **6.3 CGI**

Clinical Global Impression (CGI) Scale will also be used to assess efficacy. The CGI permits a global evaluation of the subject's improvement over time. Prior to dosing the investigator will assess the severity of the subject's condition using a CGI-Severity (CGI-S) Scale. During the Dose Optimization Period and the Double Blind Period, the investigator will assess the subject's improvement relative to symptoms prior to dosing, using the CGI-Improvement (CGI-I) Scale. CGI ratings will be completed with respect to ADHD symptoms.

### **6.4 Conners' Parent Rating Scale Revised Short Form (CPRS-R:S)**

The CPRS-R:S is a standard instrument for the assessment of ADHD in children and adolescents. It evaluates problem behaviors as reported by the parent or alternative caregivers. The CPRS-R:S contains 27 items and covers a subset of the subscales and items on the long parent form. Scales include: oppositional, cognitive problems/inattention, hyperactivity, and ADHD index.

### **6.5 Wechsler Abbreviated Scale of Intelligence – Second Edition (WASI II)**

The WASI is a general intelligence, or IQ test designed to assess specific and overall cognitive capabilities. The Wechsler Abbreviated Scale of Intelligence - Second Edition (WASI-II), a revision of the WASI, provides a brief, reliable measure of cognitive ability for use in clinical, educational and research settings. The Two-Subtest Form (Vocabulary and Matrix Reasoning) to be employed in this trial, takes about 15 minutes to administer.

### **6.6 M.I.N.I.-KID/M.I.N.I.-KID-P 6.0**

Amendment 4: Version 5.0 May-08-2013  
Amendment 3: Version 4.0 December-11-2012  
Amendment 2: Version 3.0 October-31-2012  
Amendment 1: Version 2.0 August-02-2012  
Final Protocol May-25-2012

The M.I.N.I. International Neuropsychiatric Interview (M.I.N.I. 6.0), a short, structured diagnostic interview developed in 1990 by psychiatrists and clinicians in the United States and Europe for DSM-IV and ICD-10 psychiatric disorders, will be employed at screening to rule out co-existing exclusionary psychiatric conditions. With an administration time of approximately 15 minutes, the M.I.N.I. 6.0 (10/10/10) is the structured psychiatric interview of choice for psychiatric evaluation and outcome tracking in clinical psychopharmacology trials and epidemiological studies. Use of either the child or parent version is at the discretion of the investigator.

### **6.7 10-Point Pain Scale**

A 10 -point pain scale will be employed on laboratory classroom days to evaluate all discomfort scores greater than 0. For subjects 6-11 the Wong-Baker FACES Pain Scale will be used and for subjects 12-17 a Visual Analog Scale (VAS) will be used (See Appendix 6 for examples).

### **6.8 Medical History and Physical Examination**

A complete medical history including a history of ADHD will be collected at the screening visit.

A complete physical examination will be performed by the Investigator or designee. The complete physical examination will include observation and examination of the subject's general appearance, skin, eyes, ears, nose throat, lungs, heart, abdomen, lymph nodes, extremities, nervous system, and musculoskeletal system. Significant findings at Screening, which have a start date before the date of signing of the informed consent, will be recorded as medical history. Any new findings with a start date after the signing of the informed consent or findings showing worsening of a pre-existing condition will be recorded as AEs.

### **6.9 Vital Signs**

Vital sign measurements will consist of oral body temperature, sitting respiratory rate, and sitting systolic and diastolic blood pressure, and sitting pulse after a minimum of 5 minutes rest.

Blood pressure (BP) should be determined by cuff (manual or automated is acceptable; however the same method should be used throughout the study). A BP cuff suitable to the subject's arm should be used for all BP measurements. All BP measurements should be taken from the same arm and whenever possible, performed by the same site personnel throughout the study.

Amendment 4: Version 5.0 May-08-2013

Amendment 3: Version 4.0 December-11-2012

Amendment 2: Version 3.0 October-31-2012

Amendment 1: Version 2.0 August-02-2012

Final Protocol May-25-2012

Vital signs will be evaluated to determine whether the values are: 1) Normal; 2) Abnormal, Not Clinically Significant and 3) Abnormal, Clinically Significant. Clinically significant values should be recorded as AEs and will be followed to resolution or up to 30 days following patch removal, whichever comes first.

### **6.10 Height and Weight**

Body height and weight will be measured with the subject in ordinary indoor clothing without shoes

### **6.11 Body Mass Index (BMI)**

BMI will be calculated at screening. The CDC growth charts in Appendices 3 and 4 will be used to verify study eligibility.

### **6.12 Electrocardiogram**

A standard 12-lead ECG should be obtained after the subject has been in a supine position for at least 5 minutes. ECGs will be recorded using a standard cardiograph on standard ECG paper.

Any ECG which demonstrates a clinically significant abnormality during the study will be repeated within 24 hours. If the abnormality persists, ECGs will be obtained daily until the changes have resolved or are satisfactorily explained. ECGs will be interpreted by a qualified physician and evaluated to determine whether the ECG findings are: 1) Normal; 2) Abnormal, Not Clinically Significant and 3) Abnormal, Clinically Significant. Clinically significant ECG findings should be recorded as AEs and will be followed to resolution or up to 30 days following patch removal, whichever comes first.

### **6.13 Columbia-Suicide Severity Rating Scale (C-SSRS)**

The C-SSRS facilitates prospective, systematic monitoring for emergence of suicidality within clinical trials and it is a low-burden, clinician-administered tool that covers the wide spectrum of suicidality from ideation to behavior. A training tool will be supplied to the site by the sponsor. The site will document training of selected staff members and file the training certificates in the trial master file.

Amendment 4: Version 5.0 May-08-2013

Amendment 3: Version 4.0 December-11-2012

Amendment 2: Version 3.0 October-31-2012

Amendment 1: Version 2.0 August-02-2012

Final Protocol May-25-2012

## **6.14 Clinical Laboratory Evaluations**

A central laboratory will be used to analyze all blood and urine samples with the exception of the urine pregnancy tests. Subjects for whom a urine pregnancy test is required may not begin treatment until results of the test are known. Results of the pregnancy test must be negative for the subject to be eligible for participation in the study. Subjects will not be required to fast prior to collecting blood for laboratory testing. The clinical laboratory assessment will consist of the following:

Hematology: hemoglobin, hematocrit, white blood cell count, red blood cell count, platelet count, basophils, neutrophils, bands, lymphocytes, monocytes, and eosinophils.

Serum Chemistry: total bilirubin, alkaline phosphatase, alanine transaminase, aspartate transaminase, creatine phosphokinase, lactate dehydrogenase, blood urea nitrogen, creatinine, glucose, total protein, albumin, sodium, potassium, chloride, calcium, inorganic phosphorus, and Hemoglobin A1c.

Urinalysis: specific gravity, pH, protein, glucose, ketones, bilirubin, and blood.

Urine drug screen and cotinine (screening only).

The investigator will evaluate all laboratory test values that are outside the normal range and will indicate whether these values are clinically significant or not clinically significant. Clinically significant laboratory values should be recorded as AEs and will be followed to resolution or up to 30 days following patch removal, whichever comes first.

All abnormal laboratory tests considered to be clinically significant by the investigator may be repeated at the investigator's discretion to rule out the possibility of laboratory error.

## **6.15 Patch Application and Removal**

On home days, patches will be applied daily by the subject/parent/caregiver. Demonstration and instructions on patch application will be provided by a study staff member at the Baseline (Day 0) visit. Patches will be applied to the subject's hip and alternated left and right daily. On classroom days (Day 35, Day, 42, and Day 49), the patches will be applied by subject/parent/caregiver/site personnel in the clinic. See Appendix 2 for complete patch

Amendment 4: Version 5.0 May-08-2013

Amendment 3: Version 4.0 December-11-2012

Amendment 2: Version 3.0 October-31-2012

Amendment 1: Version 2.0 August-02-2012

Final Protocol May-25-2012

application and removal instructions. Subject/parent/caregiver will be instructed to save the used patches and bring them to the clinic at their next clinic visit. Site staff will collect all used patches.

## 6.16 Dermal Evaluations

A trained individual will evaluate the d-ATS application site for adhesion of the patch to the skin and for any discomfort or irritation caused by it. The evaluator will observe the skin directly under the clear d-ATS, without removing the system, and interview the subject. Post-removal, the evaluator will assess the application site and the surrounding area for irritation and adhesive residue. Dermal evaluations must be completed in accordance with the instructions listed below.

In order to ensure reliability between successive ratings, a dedicated evaluator should follow each subject through the completion of the study. If this is not possible, then every effort must be made to limit the number of evaluators to two. *Signs and/or symptoms of discomfort or irritation related to the patch should NOT be recorded as AEs, unless (i) they occur at a site different from the application site; (ii) if the subject or patch application site is discontinued prematurely from the study due to discomfort or irritation at the patch site; (iii) the symptoms of discomfort or irritation are so severe that in the investigator's judgment it should be recorded as an AE; (iv) the subject requires a concomitant therapy to treat discomfort or irritation. If discomfort or irritation is recorded as an AE then the AE will be followed to resolution or up to 30 days following patch removal, whichever comes first.*

Spontaneous complaints of irritation or discomfort at the patch application site at times that are unscheduled will be also recorded. Spontaneous reports might include but are not limited to the following: initial complaint irritation or discomfort, exacerbation of an existing irritation or discomfort. The time elapsed between the unscheduled evaluation and d-ATS application must be recorded. At times when the laboratory classroom is scheduled on the same hour as a dermal evaluation, the dermal evaluation may take place up to 10 minutes prior to the start of the classroom.

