### **6.16.2 Discomfort**

While assessing discomfort, the evaluator must ask the subject, "Are you experiencing any discomfort related to the patch?" If the answer is "no", the overall level of discomfort will be rated as zero. If the answer is "yes", the evaluator will ask the subject to rate the discomfort as mild, moderate, or severe. If the discomfort is mild, moderate, or severe, the evaluator will probe the subject further, i.e. "Describe your discomfort". The type of discomfort should be specified

Amendment 4: Version 5.0 May-08-2013

Amendment 3: Version 4.0 December-11-2012

Amendment 2: Version 3.0 October-31-2012

Amendment 1: Version 2.0 August-02-2012

Final Protocol May-25-2012

and recorded i.e., itching, burning, or other. Any discomfort will be followed to resolution. Discomfort should be recorded and rated according to the scale in Table 2.

**Table 2:** Experience of Discomfort

Score	Definition
0	No discomfort
1	Mild discomfort
2	Moderate but tolerable discomfort
3	Severe, intolerable discomfort
4	Patch not present

For discomfort scores greater than 0, discomfort will also be evaluated after d-ATS patch application on Day 35, Day 42, and Day 49 using the 10-point Wong-Baker Faces or Visual Analog Scale (age dependent). A  $\pm$  15 minute window is permissible.

Additionally, every day at home, prior to patch removal, discomfort will be evaluated by the subject/parent/caregiver. Discomfort will be evaluated according to a Yes/No question. Subject will be required to answer the following questions:

1. Are you experiencing any discomfort? Yes/No
2. If 'Yes', then describe your discomfort? Burning, itching or other

***NOTE: Signs and/or symptoms of discomfort related to the patch should NOT be recorded as AEs, unless they occur at a site different from the application site or if the subject or patch application site is discontinued prematurely from the study due to discomfort at the patch site or the symptoms of discomfort are so severe that in the investigator's judgment it should be recorded as an AE. If discomfort is recorded as an AE then the AE will be followed to resolution or up to 30 days following patch removal, whichever comes first.***

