**NOTE: Signs and/or symptoms of skin irritation related to the patch should NOT be recorded as AEs, unless they occur at a site different from the application site or if the subject or patch application site is discontinued prematurely from the study due to irritation at the patch site and/or symptomatic intolerable irritation or the symptoms of irritation are so severe that in the investigator's judgment it should be recorded as an AE. If irritation is recorded as an AE then the AE will be followed to resolution or up to 30 days following patch removal, whichever comes first. In addition, a score of "N" (none) for the Other Effects Scale will be added as an option on the eCRF when no other effects are observed. This must also be noted on a source document.**

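### Protocol 6.16 makes a patch-site reaction that needs concomitant therapy an adverse event, but the notes in 6.16.2 and 6.16.3 omit that exception and nothing says which rule prevails

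*Protocol*

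**What the plan says.** Protocol 6.16 (Dermal Evaluations) sets a default against adverse event recording. Patch-site signs and symptoms "should NOT be recorded as AEs, unless (i) they occur at a site different from the application site" or meet one of three further conditions. The last of the four is sufficient by itself: "iv) the subject requires a concomitant therapy to treat discomfort or irritation".

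Two subsections restate the default in emphasised notes.

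- The note in 6.16.2 begins "Signs and/or symptoms of discomfort related to the patch should NOT be recorded as AEs, unless they occur at a site" away from the application site. It then allows early discontinuation because of discomfort, or discomfort the investigator judges severe enough to record.
- The note in 6.16.3 begins "Signs and/or symptoms of skin irritation related to the patch should NOT be recorded as AEs, unless they occur at a site" away from the application site. It then allows early discontinuation, mentions symptomatic intolerable irritation, and ends with the same severity judgment.

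Neither note mentions a need for treatment.

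All three places say that a reaction recorded as an adverse event is followed until it resolves or until 30 days after patch removal, whichever is earlier. Separately, 6.16.2 says that any discomfort is followed to resolution.

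SAP 7.7.1 summarises treatment-emergent adverse events overall, by relationship to treatment, by discontinuation and by intensity, in the Safety population. It works from events as recorded.

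**The concern.** Safety is a primary objective (Protocol 4), and the product is a patch compared with a placebo patch of identical appearance (Protocol 7.1.2). A local reaction that needed treatment is among the most informative local safety events such a trial can report. Of the exceptions in 6.16 that apply to a child who stays in the study with a reaction at the application site, need for therapy is the only one tied to an observable fact. The other is a judgment of severity.

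If staff work from the notes, a treated but tolerable reaction is left out of the adverse event tables. If they work from 6.16, it is included. The analysis cannot repair this afterwards, because the SAP has no rule that turns an unrecorded reaction into an event.

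**Working it through.** No arithmetic applies: the point uses no rate, sample size or test. The check is a comparison of the three lists, then a search for a rule that decides between them.

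**Step 1. The exceptions side by side.**

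| Reason to record as an adverse event | 6.16 | 6.16.2 note | 6.16.3 note |
|---|---|---|---|
| Reaction away from the application site | yes | yes | yes |
| Subject or site discontinued early because of it | yes | yes | yes |
| Severe enough in the investigator's judgment | yes | yes | yes |
| Concomitant therapy required | yes | no | no |
| Symptomatic intolerable irritation | no | no | yes |

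The last row is itself unclear. In 6.16.3 the phrase can be read as a separate exception or as a second reason for discontinuation.

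**Step 2. Are the lists closed?** Yes. Each is a prohibition followed by named exceptions, with no wording that marks them as examples. The note in 6.16.3 says such signs "should NOT be recorded as AEs, unless they occur at a site different from the application site" or meet one of the conditions that follow.

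**Step 3. Does anything give one list precedence?** Section 6.16 says "Dermal evaluations must be completed in accordance with the instructions listed below". Its own list and both notes come below that sentence, so it does not choose between them. Protocol 6.17, 7.4.1 and 8.4.1 and SAP 5, 7.6 and 7.7.1 contain no rule of precedence.

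**Step 4. Which reactions fall in the gap?** A reaction is classified differently only if it is (a) at the application site, (b) treated with a concomitant therapy, (c) not a cause of discontinuation, and (d) not judged severe or, for irritation, intolerable. Under 6.16 it is an adverse event by the fourth exception. Under the notes no exception is met.

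**Step 5. Does follow-up change?**

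- Discomfort: no. 6.16.2 follows it to resolution whatever its status.
- Irritation: yes. The only stated follow-up to resolution or 30 days, in 6.16 and in the 6.16.3 note, applies once the irritation has been recorded as an adverse event.

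**Step 6. Do other outputs supply the missing count?** Only in part.

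- The irritation summaries in SAP 7.6.1.2 use in-clinic assessments. The visit text schedules site-graded irritation at Visit 5 (Protocol 5.3.4.2) and Visits 6 and 7 (5.3.5.3).
- Home diary entries are listed (SAP 7.6.1.2 and 7.6.1.3). Their questions ask whether there is irritation or discomfort and of what type.
- Neither the grading scales nor the diary questions record whether treatment was needed.
- Concomitant therapy is recorded at each visit, then summarised and listed (SAP 7.4.2).

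The reaction and the medication can therefore both appear in listings, while the event is absent from the adverse event counts.

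**The case against.** The strongest reply is that the gap is narrow and the information is not lost. Every evaluator meets the full four-item list in 6.16 before reaching the notes. Both notes keep a judgment route, under which the investigator may record a reaction when "the symptoms of discomfort are so severe" (or, in 6.16.3, the irritation is) that it should be an adverse event. An investigator who decides to treat may well use that route. Irritation is also observed whether or not it is an adverse event: the home diary has daily inspection, diaries are reviewed at visits, telephone calls between visits ask about adverse events and therapy, and unscheduled complaints are recorded. Safety analyses are descriptive only, and the SKAMP analysis is untouched. A check linking medications to events may already exist in the Data Management Plan, which SAP 9.1 and 9.2 cite but which was not supplied.

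Most of this stands, and it limits the point. It does not remove it. The judgment route turns on severity, whereas 6.16 makes need for therapy sufficient without it. Continued observation is not a stated follow-up to resolution. Listings do not enter the TEAE counts. The order of the paragraphs does not settle which list governs, particularly when the later lists are emphasised notes placed with the grading instructions.

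**Conclusion.** The three lists conflict in current text, and the conflict should be resolved. It affects which events are counted in a primary safety objective, not the efficacy result. If the notes are followed, the TEAE, treatment-related and by-intensity counts could be understated by the reactions described in step 4 of the working.

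A reader might infer more than the documents support:

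- **That the notes bar every treated reaction from being an adverse event.** They do not. Severity, discontinuation and location remain as routes, and irritation may also qualify as intolerable.
- **That children who needed treatment lose follow-up.** This is untrue for discomfort. For irritation, what is missing is a stated follow-up to resolution or 30 days when no adverse event is recorded; observation continues.
- **That sites will in fact count differently.** They could. The documents do not show that they do.
- **That the effect has a calculable size.** The documents give no rate of treated reactions. Multiplying an assumed rate by the 90 randomised subjects would only return the assumption. It would also use the wrong denominator, because TEAEs are summarised in the Safety population, which includes subjects dosed in the open-label period who were never randomised.

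The conclusion rests on the lists being read as closed and on no supplementary site instruction having already settled the matter.

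**What to change.** Reconcile 6.16 and the notes in 6.16.2 and 6.16.3 to one identical list of exceptions that includes need for concomitant therapy. Decide whether symptomatic intolerable irritation stays and, if it does, state whether it is an exception of its own or a reason for discontinuation. The simplest form is to keep the list in 6.16 and have each note refer to it.

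If the Data Management Plan does not already have it, add a query, run on blinded data before database lock, for any concomitant medication given for an application-site reaction that has no linked adverse event record.

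The cost is revised wording in the affected paragraphs, a memo to sites and, if needed, one data-management query. The downside is that the reported application-site adverse event rate may be slightly higher. No dose, treatment rule or efficacy analysis changes.
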